8.1. Derivation of Efficacy Endpoints

8.1.1. Best Percentage Change in Tumor Size

Best percentage change in tumor size is defined as the largest decrease or smallest increase (in the absence of a decrease) in the sum of diameters of the TLs prior to progression or last evaluable assessment in the absence of progression.

- If a patient receives another anti-cancer therapy prior to progression, then data up until the least evaluable TL assessment prior to the start of subsequent therapy will be included
- If a patient does not have any evaluable post-treatment TL assessments to allow a derivation of best percentage change from baseline, they will be excluded from analysis

8.1.2. Objective Response Rate (ORR)

Objective Response Rate (ORR) is defined as the proportion of patients with a confirmed response of CR or PR (i.e., 2 visit responses of either CR or PR at least 4 weeks apart) according to RECIST v1.1 criteria. This analysis will be limited to patients with measurable disease.

• Response will be assessed based on all evaluable assessments up to and including progression per RECIST v1.1. Responses occurring following subsequent anti-cancer therapy will be excluded from the assessment of ORR but will be included in the listing.

8.1.3. Best Overall Response Rate

Best Overall Response Rate is defined as the proportion of patients with confirmed or unconfirmed response of CR or PR based on best overall response by investigators across all visits. Unconfirmed CR or PR will be defined as those patients with CR or PR only reported once in overall tumor assessment form by the Investigators according to RECIST 1.1.

Note that the unconfirmed CR or PR (assessed by investigator) is added as a response criterion in addition to protocol defined confirmed CR or PR, to identify signal of anti-tumor activity for the treatment.

8.1.4. Clinical Benefit Rate (CBR)

CBR is defined as the proportion of patients with a best overall response of CR or PR according to RECIST v1.1 based on Investigator's assessment or duration on treatment of at least 16 weeks without evidence of progression.

CBR will be defined for patients in efficacy population only.

8.1.5. Duration of Response (DOR)

Duration of Response (DOR) will be derived for patients with a confirmed CR or PR only. DOR is defined as the time from the date of the earliest qualifying response (CR or PR) to the date of disease progression or death for any cause, whichever occurs earlier. Note, the end of response should coincide with the date of progression or death from any cause used for the PFS endpoint.

Given responses are required to be confirmed, the date of earliest qualifying response is the latest date for the visit where the initial overall visit assessment of CR/PR was observed rather than the confirmation visit assessment.

For patients who are alive without disease progression following response, DOR will be censored on the date of the last evaluable tumor assessment, last follow-up for disease progression, or data cut-off date, whichever occurs first. Handling of death without PD will be similar to PFS.

Table 4 gives the details rules of defining censoring/event for DOR.

Table 4: Censoring rule for Duration of Response (DOR) based on radiographical tumor assessment or death

Situation	Date of Censoring or Date of Event	DOR (weeks)	Censor
Documented disease progression (PD) before data cutoff date	Date of first PD	(Date of first PD – Date of first PR/CR + 1)/7	0
No PD, but death date before data cutoff date, or death date within 12 weeks after last adequate tumor assessment	Date of death	(Date of death – Date of first PR/CR + 1)/7	0
No PD and no death before data cutoff date, or death date beyond 12 weeks after last adequate tumor assessment	Date of last adequate tumor assessment ^a before data cutoff	(Date of last adequate tumor assessment ^a – Date of first PR/CR + 1)/7	1

^a Adequate disease assessment is defined as a response assessment other than "not assessed" or "not evaluable."

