2.2.2. Efficacy Endpoints

Best percentage change in tumor size: defined as the largest decrease or smallest increase (in the absence of a decrease) in the sum of diameters of the target lesions (TLs) prior to progression or last evaluable assessment in the absence of progression.

[figure not shown]
- Objective response rate (ORR): defined as the proportion of patients with confirmed best overall response of complete response (CR) or partial response (PR) (i.e., 2 subsequent responses of either CR or PR at least 4 weeks apart) according to RECIST v1.1.
- **Best overall response rate**: defined as the proportion of patients with **confirmed or unconfirmed** response of CR or PR based on best overall response by investigators across all visits. Unconfirmed CR or PR will be defined as those patients with CR or PR only reported once in overall tumor assessment form by the Investigators according to RECIST 1.1.
- Clinical benefit rate (CBR): defined as the proportion of patients with a best overall response of CR or PR according to RECIST v1.1 based on Investigator's assessment, or duration on treatment of at least 16 weeks without evidence of progression.

Duration of response (DOR, applicable only to patients with confirmed CR or PR): defined as the time interval between the date of the earliest qualifying response (CR or PR) and the date of disease progression or death for any cause, whichever occurs earlier.

For patients who are alive without disease progression following response, DOR will be censored on the date of last evaluable tumor assessment.

- **Progression-free survival (PFS)**: defined as the time from the first day of study treatment administration (Day 1) to disease progression as defined by RECIST v1.1 or death from any cause.
 - Patients who are alive and free from disease progression will be censored at the date of their last tumor assessment.
 - Any patient who dies in the absence of progression, and the death is >12 weeks after the last evaluable tumor assessment, will be censored for PFS at the date of their last evaluable tumor assessment. More details are provided in Section 8.1.9 and Table 8.

Detailed derivation of the endpoints can be found in Section 36.

[figure not shown]

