8.1.8. Progression Free Survival (PFS)

Progression-Free Survival (PFS) is defined as the time from the first day of study drug administration (Day 1) to disease progression as defined by RECIST v1.1 criteria or death from any cause.

TL, NTL and new lesion assessments may be performed on different dates. The following rules will be applied for determine progression and censoring dates:

Date of progression will be determined based on the earliest of the dates of the component that triggered the progression. For example, if progression was due to a new lesion only then the date of the new lesions would be used. If progression was due to TLs and a new lesion, then the earliest of the TL and new lesion dates would be used.

Patients who are alive and free from disease progression will be censored at the date of their last evaluable tumor assessment prior to or equal to the data cut off date.

Any patient who dies in the absence of progression after 2 or more missed assessments will be censored at the date of their last radiographic tumor assessment. Specifically, if the death date is >12 weeks from the last tumor assessment, the death date will not be used for the calculation of PFS.

If a patient has no baseline tumor assessment/no post dose tumor assessments then they will be censored at 0 days for PFS, unless they died within 12 weeks from the date of first dose (and also before cut-off), in which case their death date will be used as a PFS event.

Table 5 gives the details rules of defining censoring/event for PFS.

PFS at 6 months will be reported based on KM methods as the number and % of patients estimated to be progression free at 6 months.

Table 5: Censoring Rule for time-to-event analyses (PFS) based on radiographical tumor assessment or death

Situation	Date of Censoring or Date of Event	Censor
Documented disease progression (PD) before data cutoff	Date of first PD	0
No PD, but death date is within 12 weeks from the last adequate post-baseline assessment ^a	Date of death	0
No PD, no post-baseline assessment, and death date is within 12 weeks from the date of first dose	Date of death	0
No PD, no post-baseline assessment ^a , and death date > 12 weeks from the date of first dose	Date of the first dose	1
No PD, no post-baseline assessment ^a , and no death	Date of the first dose	1

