No PD, Death date > 12 weeks from the last adequate post-baseline assessment ^a (e.g., 2 or more consecutive missed scheduled disease status assessments and the gap > 12 weeks)	Date of last adequate tumor assessment ^a	1
No PD or death, but with last adequate assessment ^a before data cut off	Date of last adequate tumor assessment ^a	1

^a Adequate disease assessment is defined as a response assessment other than "not assessed" or "not evaluable."

This Censoring Rule is used for the data after implementation of data cut off.

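### SAP Table 4 codes the same late death without progression as both a duration-of-response event and a censored observation

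*SAP*

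**What the plan says.** SAP section 8.1.5, Table 4, has three rows. The first covers documented progression. The second assigns an event at the date of death (Censor 0) to "No PD, but death date before data cutoff date, or death date within 12 weeks after last adequate tumor assessment". The third assigns censoring at the last adequate assessment (Censor 1) to "No PD and no death before data cutoff date, or death date beyond 12 weeks after last adequate tumor assessment".

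The text above the table ties DOR to PFS twice: "Handling of death without PD will be similar to PFS", and "the end of response should coincide with the date of progression or death from any cause used for the PFS endpoint". It then refers to Table 4 for the detailed rules.

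For PFS, section 8.1.8 and Table 5 censor a death without progression that falls more than 12 weeks after the last adequate assessment. Table 5 also carries a note: "This Censoring Rule is used for the data after implementation of data cut off". Table 4 has no such note.

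The DOR definition in section 2.2.2 makes death from any cause an event and describes censoring only for survivors: "For patients who are alive without disease progression following response, DOR will be censored on the date of last evaluable tumor assessment". The PFS definition in the same section does state the 12-week exception. It sends the reader to section 8.1.9 and Table 8 for details, whereas the rule stands in section 8.1.8 and Table 5.

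Section 8.1.8 explains the PFS limit first as a count of missed scans, "Any patient who dies in the absence of progression after 2 or more missed assessments will be censored", and then as a time, "Specifically, if the death date is >12 weeks from the last tumor assessment".

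**The concern.** A censoring table must place every patient in exactly one row. Table 4 does not: one kind of death receives opposite codes and different dates. A programmer following the second row and a validator following the third could each cite the SAP, and PFS and DOR could end on different dates for one patient.

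Such deaths can be expected in the data. The Protocol synopsis (Efficacy) lets scans stop at the start of subsequent anticancer treatment, while SAP section 3.2 continues survival follow-up for up to 12 months after the end of treatment. Neither table has a row for new therapy, so a responder who switches treatment without progression and later dies is classified by the rows at issue.

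A smaller matter is that section 8.1.8 presents more than 12 weeks as the meaning of two missed scans, which the scan schedule supports only early in the study.

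**Working it through.** **1. Table 4 read literally.** Let D be death, C the data cutoff and L the last adequate scan, all in study weeks, with no progression. Row 2 applies if D is before C *or* D − L ≤ 12. Row 3 applies if there is no death before C *or* D − L > 12. The weeks below are illustrative.

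| Case | L | D | C | D − L | Rows met |
|---|---|---|---|---|---|
| Death before cutoff, within 12 weeks | 18 | 28 | 60 | 10 | 2 |
| Death before cutoff, beyond 12 weeks | 18 | 40 | 60 | 22 | **2 and 3** |
| Death after cutoff, within 12 weeks | 54 | 62 | 60 | 8 | **2 and 3** |
| Death after cutoff, beyond 12 weeks | 54 | 75 | 60 | 21 | 3 |
| No death | 18 | – | 60 | – | 3 |

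**2. Size for one patient.** Table 4 computes DOR as (end date − date of first PR/CR + 1)/7. Take first PR at week 6 (day 42), last adequate scan at week 18 (day 126) and death at week 40 (day 280).

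- Row 2: (280 − 42 + 1)/7 = 239/7 = 34.1 weeks, event.
- Row 3: (126 − 42 + 1)/7 = 85/7 = 12.1 weeks, censored.
- Difference: 154/7 = 22.0 weeks, with opposite event status.

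Under Table 5 this patient's PFS is censored at the week-18 scan. Row 3 agrees with that; row 2 does not.

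**3. With the event row requiring both conditions.** Row 2 becomes D before C *and* D − L ≤ 12, and row 3 its complement. The five cases then fall in rows 2, 3, 3, 3 and 3, one row each.

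**4. When the main overlap can arise.** The widest planned spacing is 9 weeks, and the ±7-day windows can stretch it to 9 + 1 + 1 = 11 weeks. With every scan done and evaluable until progression or death, no death falls more than 12 weeks after the last scan. The overlap before cutoff therefore needs a stopped, missed or non-evaluable scan.

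**5. Two missed scans in weeks.** The Protocol synopsis schedules follow-up scans every 6 weeks for three assessments, then every 9 weeks: weeks 6, 12, 18, 27, 36, 45 and so on.

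| Last scan (week) | Second scheduled scan after it (week) | Gap (weeks) | Range with ±7-day windows (weeks) |
|---|---|---|---|
| Baseline | 12 | 12 | 11–13 |
| 6 | 18 | 12 | 10–14 |
| 12 | 27 | 15 | 13–17 |
| 18 | 36 | 18 | 16–20 |
| 27 | 45 | 18 | 16–20 |

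The stated 12 weeks is reproduced as 2 × 6 for a last scan at baseline or week 6 only. On nominal dates, a death more than 12 but less than 15 weeks after a week-12 scan, or more than 12 but less than 18 weeks after a scan at week 18 or later, is censored with one scheduled scan missed. Because response must be confirmed at least 4 weeks later, a confirmed responder's last scheduled scan is nominally week 12 or later, so for DOR the equivalence does not hold at any scheduled last scan.

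**The case against.** The strongest reply is that the SAP shows what was meant. The text of 8.1.5 aligns DOR with PFS, and Table 5 plainly censors these deaths. If every death before cutoff were an event, the 12-week condition in row 2 would be almost idle and the second half of row 3 would contradict it. Section 2.2.2 is a summary that defers to a later derivation, so its missing exception is incompleteness rather than a rival rule. The overlap after cutoff is nearly theoretical, since row 3 already uses the last assessment before cutoff and Table 5's note indicates analysis of cut data.

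Much of this stands: censoring is the better-supported reading, and the overlap after cutoff disappears once the cut is applied. It does not remove the error. Table 4 is the detailed rule that will be programmed, its event row contradicts the text above it, and the 2.2.2 definition read alone supports that row.

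Three stronger inferences are tempting, and the documents do not support them:

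- *That the PFS rule is itself ambiguous.* Section 8.1.8 and Table 5 both apply more than 12 weeks. The missed-scan wording in Table 5 is only an example, so the mismatch lies in the stated rationale.
- *That 12 weeks is an error and must follow the scan schedule.* A fixed, pre-specified limit is workable. Replacing it would be a change of analysis preference.
- *That DOR results are unreliable in general.* Only the narrow group of deaths described above is affected.

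**Conclusion.** Table 4 is wrong as written and should be corrected. That conclusion needs no assumption beyond reading its two rows literally. In the illustrative patient the choice of row moves DOR by 22.0 weeks and reverses its event status.

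The overall effect is limited. DOR is secondary and descriptive, and no test or sample size depends on it. The number affected cannot be derived from the documents, because it depends on how many confirmed responders stop or miss scans before progression and then die; with complete, evaluable scanning it is zero for deaths before cutoff. The effect matters mainly in small responder groups, where one patient can move a median. Section 8.2 summarises efficacy by dose level within each module, so small groups are likely.

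The missed-scan explanation in 8.1.8 is a minor inconsistency that leaves the operative PFS rule intact.

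**What to change.** 1. **Table 4, event row:** *No PD; death before the data cutoff and no more than 12 weeks after the last adequate assessment.*
2. **Table 4, censoring row:** *No PD; either no death before the data cutoff, or death more than 12 weeks after the last adequate assessment.*
3. Add to Table 4 the note under Table 5 that the rule is applied after the data cut.
4. State the same 12-week exception in the DOR text of sections 2.2.2 and 8.1.5.
5. Correct the pointer in section 2.2.2 to section 8.1.8 and Table 5.
6. Minor: keep the fixed PFS limit of more than 12 weeks, and delete or soften the missed-assessment explanation in section 8.1.8 and Table 5.

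The cost is SAP wording and the matching programming specification. No scans, data or patients are added and the PFS rule does not change. Section 1 of the SAP requires finalisation before database lock, so the correction belongs before then.

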8.1.6. Categorization of Best Tumor Response

For supportive information, the following confirmed best response categories will be derived for all patients with at least one post-baseline tumor assessment:

- Complete Response (CR): 2 visit responses of CR at least 4 weeks apart.
- Partial Response (PR): 2 visit responses of PR at least 4 weeks apart.

- Stable Disease (SD): If not confirmed CR/PR, at least one visit response of SD (or better i.e., unconfirmed CR/PR) recorded at least 6 weeks after the date of first dose of study drug.
 - To allow for the protocol window of \pm 7 days, an overall assessment of SD on or after day 35 (i.e., 5 weeks) will be regarded as stable disease.
- Progressive Disease (PD): If not CR/PR/SD, and with at least one response of disease progression
- Not-Evaluable (NE): No evidence of CR, PR, SD, or PD. Either by default or the only visit response recorded is 'NE'.

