8.2. Efficacy Analysis Methods

For overall response rate, ORR, and CBR, the number and percentage of patients along with an exact binomial 95% confidence interval (CI), using the Clopper-Pearson method, will be presented.

In general, summary of all efficacy endpoints will be provided by dose level separately for Module 1a and 1b patients.

The assessment of tumor efficacy will be based on the measurements recorded by the investigator.

A summary of the best objective response will be presented which will include the number and percentage of patients with a best response of CR, PR, SD, PD and NE.

Time-to-event endpoints (PFS) will be analyzed using the KM method and results will be summarized by the 25th, 50th and 75th percentiles, if estimable, with associated 2-sided 95% CIs. KM plots will be provided. For PFS, the number (%) of patients with an event and the number (%) of patients censored will also be presented. The rate of PFS at 16 weeks and 24 weeks will be derived from the corresponding Kaplan-Meier curves. The KM analyses for DOR may be replaced by descriptive summary of median, and quartiles with individual listing for responders if total confirmed responders are few and less than 5 patients.

Maximum reduction in tumor size will be summarized by n, mean, standard deviation, median, 25th quartile and 75th quartile, minimum and maximum. The spider plots displaying change in tumor size over time for each patient will also be provided for each module and dose/schedule group as described above.

In addition, waterfall plots showing the best percentage change from baseline (largest decrease or smallest increase in the absence of a decrease) in the sum of the TL sizes will be produced for each module by dose/schedule group indicating each patient' best objective response.

Swimmer plots will be produced for each module and dose/schedule group to show the duration of study treatment per patient with indicators for timing of response, progression or death, where applicable.

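### A patient with exactly one PR and one later CR is a confirmed responder for ORR but meets neither the CR nor the PR category in SAP 8.1.6

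*SAP*

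**What the plan says.** SAP 2.2.2 (Efficacy Endpoints) defines confirmation for ORR as "2 subsequent responses of either CR or PR at least 4 weeks apart". SAP 8.1.2 repeats the rule as "2 visit responses of either CR or PR at least 4 weeks apart". Both accept a mixed pair. Section 8.1.2 also limits ORR to patients with measurable disease and leaves out responses that follow subsequent anticancer therapy.

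SAP 8.1.6 (Categorization of Best Tumor Response) derives confirmed best-response categories, which it describes as supportive. Its first two lines are "Complete Response (CR): 2 visit responses of CR at least 4 weeks apart" and "Partial Response (PR): 2 visit responses of PR at least 4 weeks apart". Its SD line takes patients without a confirmed CR or PR who have "at least one visit response of SD (or better i.e., unconfirmed CR/PR) recorded at least 6 weeks after the date of first dose", with the 6 weeks relaxed to day 35 to allow for the scan window. PD and NE follow.

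SAP 8.2 then plans a summary of best objective response giving the "number and percentage of patients with a best response of CR, PR, SD, PD and NE", and waterfall plots that "will be produced for each module by dose/schedule group indicating each patient' best objective response". Section 8.2 does not cite 8.1.6, but it uses the same five categories, and 8.1.6 is the only section that derives them.

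**The concern.** Two sections of one SAP use different rules for what confirms a response. The ORR rule lets a CR confirm an earlier PR. The 8.1.6 rule does not: it requires a like pair and contains no wording equivalent to PR or better. A patient whose PR deepens to a CR, with no further scan showing either, would count in the ORR numerator. Under SAP 8.1.5, read with the ORR meaning of confirmed, that patient would also have a duration of response. In the best-response summary the same patient would appear as stable disease or nowhere.

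At stake is agreement between displays in one report. ORR and the CR+PR rows should describe the same responders. The reporting groups are small and preliminary efficacy is one input to the RP2D choice (SAP 3.2.2), so a one-patient disagreement would be visible and would need explaining.

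**Working it through.** No sample-size, power or alpha figure is involved, so the check applies the two rules side by side.

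**Inputs**
- ORR rule (SAP 2.2.2, 8.1.2): two visits, each CR or PR, at least 28 days apart.
- Best-response rule (SAP 8.1.6), in order: CR+CR at least 28 days apart gives CR; otherwise PR+PR at least 28 days apart gives PR; otherwise any visit of SD or better on or after day 35 gives SD; otherwise PD; otherwise NE.
- Scan schedule (protocol synopsis, Efficacy): every 6 weeks ± 7 days for the first three assessments, then every 9 weeks.

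**Can the sequence occur on schedule?** The shortest gap between two consecutive 6-weekly scans is 42 − 7 − 7 = 28 days, which still meets the 4-week requirement. A PR at one scheduled scan and a CR at the next therefore always satisfies the ORR rule.

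**Worked sequences** (scans at days 42, 84, 126, 189)

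| Sequence | ORR responder | 8.1.6 category, read literally |
|---|---|---|
| PR, CR, PD | yes | SD |
| PR, CR | yes | SD |
| SD, PR, CR, PD | yes | SD |
| PR, SD, CR, PD | yes | SD |
| PR, CR, CR | yes | CR |
| PR, PR, CR | yes | PR |

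**Enumeration.** All CR/PR/SD/PD sequences of 2 to 4 visits on those days were generated, cut at the first PD, leaving out any with a PR after a CR. Of the 108 distinct sequences, 14 are ORR responders that 8.1.6 puts in SD. Each of the 14 has exactly one PR and one later CR. These are counts of possible patterns, not patient frequencies.

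**The alternative reading of the SD line.** Its condition begins "If not confirmed CR/PR, at least one visit response of SD (or better i.e., unconfirmed CR/PR". If confirmed is given the ORR meaning, the patient is confirmed and the SD line does not apply. The CR and PR lines still do not fit, so the patient has no category. SAP Appendix 3 does not settle a mixed PR-then-CR sequence.

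**Effect of the repair.** With PR redefined as not a confirmed CR, and two visits of PR or CR at least 28 days apart, all 14 sequences become PR. ORR status and CR+PR status then agree in all 108 (0 discordant). PR, CR, CR stays CR and PR, PR, CR stays PR.

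**Size.** One affected patient lowers the CR+PR share by 1/n:
- n=6 (the minimum expected at the RP2D in dose finding, SAP 8; also the backfill cap in the protocol's dose-finding text): 1/6 = 16.7 points.
- n=8 (the backfill cap in the protocol's Efficacy Analysis text): 1/8 = 12.5 points.
- n=14 (illustrative pooling of 6 dose-finding and 8 backfill patients): 1/14 = 7.1 points.

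**The case against.** The strongest reply is that little depends on this. Section 8.1.6 is labelled supportive, ORR and DOR are defined in their own sections, the study is descriptive with safety and DLTs primary, and the swimmer plots and listings would still show the response. All of that stands, and it limits the impact.

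A second reply is that SD is not the only reading. SAP 2.2.2 and 8.1.3 describe an unconfirmed response as a CR or PR reported only once, and a PR-then-CR patient has two qualifying visits. On those meanings the SD line does not admit the patient. That is a fair reading, but it leaves the patient unclassified, so the text is defective either way.

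A third concerns the plots. Section 8.2 does not cite 8.1.6, and the term best objective response is defined in protocol Appendix 4, where a footnote restricts the confirmation entries to nonrandomized studies with response as primary endpoint; here response is secondary. The link from 8.1.6 to the waterfall labels is therefore an inference from the matching categories, and the effect on the labels is conditional.

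Two stronger conclusions that a reader might draw do not hold. One is that every patient whose response deepens from PR to CR is shown as stable disease: a second PR or a second CR puts the patient in the right category. The other is that 12.5 to 16.7 points is the expected distortion. The sample-size text gives caps for backfill cohorts, SAP 8 pools backfill patients with dose-finding patients at the RP2D when applicable, and the documents give no expected number of affected patients.

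**Conclusion.** The point holds within narrow limits. SAP 8.1.6 as written cannot classify as CR or PR a patient whom 2.2.2 and 8.1.2 count as a confirmed responder, when that patient has exactly one PR and one later CR. The result is SD on the literal hierarchy, or no category if confirmed takes the ORR meaning. If such a patient occurs, CR+PR in the best-response table falls below the ORR numerator by one per patient, that is 1/n of the reported group; the waterfall labels are affected only if they use 8.1.6. The conclusion assumes that the 8.2 table uses the 8.1.6 categories, which the matching list supports but the text does not state.

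A reader might infer that the ORR estimate is biased. It is not: 8.1.2 does not draw on 8.1.6. Few patients should be affected. Label: wrong as written; low impact.

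**What to change.** Three short edits to the SAP:

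1. In 8.1.6, define confirmed PR as at least two visit responses of PR or better (PR or CR) at least 4 weeks apart that do not qualify as a confirmed CR.
2. Apply to 8.1.6 the restrictions that 8.1.2 places on ORR: measurable disease, and no responses after the start of subsequent anticancer therapy. Without this, the new PR wording alone does not guarantee that the counts agree. Protocol inclusion criterion 7 requires measurable disease, so the first restriction should rarely matter. Then state that, in the same patients, the CR+PR count must equal the ORR numerator; this also serves as a programming check.
3. In 8.2, state that the best-response table and the waterfall labels use the 8.1.6 categories.

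The cost is a few sentences and a small change to one derivation. No new data, no design change and no change to ORR are involved. It should be done before database lock, by when SAP section 1 says the plan will be final.
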